3.5. Safety analysis

All safety analyses will be performed in the SS unless otherwise specified.

Calculation rules for safety endpoints and other specific definitions are provided in [7 Appendix C](#).

Adverse events (AEs) will be graded using the National Cancer Institute (NCI) Common Terminology Criteria for Adverse Events [CTCAE version 5.0](#).

3.5.1. Adverse events

Treatment-emergent adverse events (TEAE) are defined as any AEs reported from the date of first administration of IMP to 30 days after the last date of IMP administration.

Number of events, number and percentage of patients reporting at least one event, presented by SOC and/or PT (depending on the analysis) will be provided for serious adverse events (SAE) and TEAE over the study and treatment periods, respectively.

TEAE and Serious TEAE (STEAE) will be described according to:

- Worst grade.
- Severity.
- Relationship (related to trifluridine/tipiracil, related to Futuximab/modotuximab, related to the combination) ([8 Appendix D](#)).
- Outcome (recovered/resolved, recovered/resolved with sequelae, recovering/resolving, not recovered/not resolved, fatal, unknown).
- Leading to drug withdrawal (leading to trifluridine/tipiracil withdrawal, leading to Futuximab/modotuximab withdrawal).

TEAE will be also described according to:

- Action taken regarding IMPs (drug interrupted, dose reduced, dose delayed, dose reduced or delayed, dose reduced and delayed, dose not changed, infusion rate reduced).
- TEAE related to disease progression.
- TEAE leading to death.
- TEAE related (related to trifluridine/tipiracil, related to Futuximab/modotuximab, related to the combination) leading to death
- Requirement of added therapy.

Non-STEAE (EudraCT analyses) and Non-STEAE related to IMPs will be described by SOC and PT.

Number and percentage of participants who experienced a DLT will be summarized and listed in the DLTS.

3.5.2. Death

Listing of patients who died during the treatment period or during the follow-up period will be provided.

3.5.3. Clinical laboratory evaluation

For haematological, biochemistry, coagulation and urinary parameters, descriptive statistics on value at baseline and on worst value at cycle 1 will be provided.

Number and percentage of patients for each laboratory parameter classified according to: reference ranges (< LLN/≥ LLN or ≤ ULN/≥ ULN) for non-gradable parameters except creatinine clearance, grade (Grade 0, Grade 1, Grade 2, Grade 3, Grade 4) for gradable parameters, following classes for proteinuria (Absence, Trace, Presence (+, More than one +)) and following classes for creatinine clearance (severe, mild, moderate, normal) and using shift tables from baseline to the worst (high and/or low) and last class or value under treatment will be described.

Some parameters with grade dependent on baseline value cannot be computed if there is no value at baseline.

3.5.4. Vital signs, clinical examination and other observations related to safety

Vital signs and clinical examination will be described in the SS, in terms of quantitative values for Weight (Kg), and Temperature (°C) and by classes for ECOG, BSA (m²), Heart Rate - HR (bpm), Supine Systolic Blood Pressure - SBP (mmHg), Supine Diastolic Blood Pressure - DBP (mmHg), Respiratory rate (breaths/min), and Oxygen saturation (%):

- ECOG (0, 1, 2, 3, 4) documented in the e-CRF.
- BSA (< 1.07, [1.07, 1.23), [1.23, 1.38), [1.38, 1.53), [1.53, 1.69), [1.69, 1.84), [1.84, 1.99), [1.99, 2.15), [2.15, 2.30), ≥ 2.30).
- HR (< 60, [60, 100), ≥ 100 bpm).
- SBP (< 90, [90, 140), ≥ 140 mmHg).
- DBP (< 60, [60, 90), ≥ 90 mmHg).
- Respiratory rate (< 12, [12, 18], > 18 breaths/min).
- Oxygen saturation (< 90, [90, 95], > 95 %).

Vital signs and clinical examination will be described, in terms of value at baseline, value at cycle 1 (worst value) under treatment, worst value under treatment and last post-baseline value under treatment; as well as in terms of change from baseline to cycle 1 (worst value) under treatment, to worst value under treatment, to last post-baseline value under treatment.

3.5.5. ECG

The frequency distribution (n, %) of patients with an ECG performed will be described. ECG parameters, as well as heart rate (bpm) (< 60, [60, 100), ≥ 100), will be described by classes, in terms of value at baseline and last post-baseline value under treatment. Moreover values and changes from baseline of uncorrected and corrected (Fridericia's correction ($QTcF = QT/2\sqrt{RR}$)) QT intervals, RR interval, PR interval and QRS duration will also be described in classes, considering the thresholds defined in 7.5:

≤ 450, (450, 480], (480, 500] and > 500 msec for values.

≤ 30, (30, 60] and > 60 msec for changes.

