10.1.2.6.3. Vital signs, clinical examination and other observations related to safety

10.1.2.6.3.1. Vital signs and clinical examination

Vital signs and clinical examination will be described, in terms of value at baseline, value at each post-baseline visit under treatment and last post-baseline value under treatment; as well as in terms of change from baseline to each post baseline visit under treatment and to last post-baseline value under treatment.

10.1.2.6.3.2. Electrocardiogram

ECG parameters will be described, in terms of value at baseline, value at each post-baseline visit under treatment and last post-baseline value under treatment; as well as, for quantitative endpoints, in terms of change from baseline to each post baseline visit under treatment and to last post-baseline value under treatment. Moreover, values and changes from baseline of corrected QT interval will be described in classes, considering thresholds defined in ICH E14

(*i.e.*, ≤ 450 ,] 450; 480],] 480; 500] and > 500 ms for values, and ≤ 30 ,] 30; 60] and > 60 ms for changes).

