3. STATISTICAL METHODS

3.1. General considerations

The following descriptive statistics will be provided depending on the nature of considered data:

Qualitative data: number of observed values, number and percentage of patients per class.

Quantitative data: number of observed values, mean and standard deviation, median, first and third quartiles, minimum and maximum.

Descriptive summary statistics (n, mean (SD), median, min and max) will be provided for variables measured on a continuous scale.

The frequency distribution (n, %) will be provided for variables measured on a nominal scale.

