7.5. Electrocardiogram

Change from baseline to last visit = Last absolute prolongation - Absolute prolongation at baseline.

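### SAP 3.5.5 applies the protocol's QTc classes to RR, PR and QRS, where the value classes barely discriminate and the change classes register only increases above 30 ms

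*SAP*

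**What the plan says.** Protocol 10.1.2.6.3.2 describes ECG parameters by value and, "for quantitative endpoints, in terms of change from baseline to each post baseline visit under treatment" and to the last value. It then adds, for one parameter only, that "values and changes from baseline of corrected QT interval will be described in classes, considering thresholds defined in ICH E14". The limits it lists are 450, 480 and 500 ms for values and 30 and 60 ms for changes.

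SAP 3.5.5 says ECG parameters are described by classes at baseline and at the last value. A further sentence covers values and changes of uncorrected QT and QTcF and continues: "RR interval, PR interval and QRS duration will also be described in classes, considering the thresholds defined in 7.5". One set of limits follows: "≤ 450, (450, 480], (480, 500] and > 500 msec for values", and "≤ 30, (30, 60] and > 60 msec for changes". Heart rate has separate classes in the same section.

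SAP 7.5, the cited source of the thresholds, consists of one formula: "Change from baseline to last visit = Last absolute prolongation - Absolute prolongation at baseline".

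**The concern.** The SAP takes limits that the protocol reserves for corrected QT and extends them to four more intervals: uncorrected QT, RR, PR and QRS. RR, PR and QRS are on different scales from QT. If their values nearly all fall in one class at baseline and again at the last value, the tables cannot show a shift. A PR or QRS value crossing a normal limit would not appear. Nearly every RR value would be reported in the class that signals marked prolongation for QTc.

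The change classes run in one direction. The lowest is open downwards, so it pools increases of up to 30 ms, no change and every shortening. For RR, which moves inversely with heart rate, ordinary slowing is highlighted and marked acceleration is hidden.

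It is also unclear whether numeric summaries will accompany the classes. SAP 3.1 sets general statistics for quantitative data, but 3.5.5 speaks of description by classes. The neighbouring section 3.5.4 contrasts the two forms: "in terms of quantitative values for Weight (Kg), and Temperature (°C) and by classes for ECOG" and other vital signs. It also gives each classed vital sign its own cut-offs.

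**Working it through.** The plan states no figure to reproduce. The check sorts interval values into the printed classes.

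**Inputs.** The value and change limits come from SAP 3.5.5 and match protocol 10.1.2.6.3.2. RR in ms is 60,000 divided by heart rate in bpm. The ECG footnotes to the protocol's investigation schedules (4.1.2) define QT as starting with the QRS complex and ending with the T wave. The documents give no reference ranges for PR or QRS, so I assume baseline PR of 120–200 ms and QRS of 80–120 ms.

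**RR values.** The limits 450, 480 and 500 ms convert to 60,000/450 = 133.3, 60,000/480 = 125 and 60,000/500 = 120 bpm.

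| Heart rate (bpm) | RR (ms) | Class (ms) |
|---|---|---|
| 60 | 1000 | > 500 |
| 70 | 857.1 | > 500 |
| 80 | 750 | > 500 |
| 100 | 600 | > 500 |
| 119 | 504.2 | > 500 |
| 120 | 500 | (480, 500] |
| 140 | 428.6 | ≤ 450 |

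All of the SAP's own heart-rate classes below 60 and from 60 to under 100 bpm, and the part of its top class below 120 bpm, fall in the top RR class.

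**RR changes.**
- 70 to 65 bpm: 923.1 − 857.1 = +65.9 ms (unrounded inputs), class > 60.
- 70 to 90 bpm: 666.7 − 857.1 = −190.5 ms (unrounded inputs), class ≤ 30.

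RR has risen by exactly 60 ms when heart rate falls to 60,000/(60,000/HR₀ + 60), where HR₀ is the baseline rate. Any further slowing puts the change in the top class.

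| Baseline HR₀ (bpm) | Rate at +60 ms (bpm) | Fall (bpm) |
|---|---|---|
| 60 | 56.6 | 3.4 |
| 70 | 65.4 | 4.6 |
| 80 | 74.1 | 5.9 |
| 100 | 90.9 | 9.1 |

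**QRS values.** By the protocol's definition QRS is part of QT, so QRS cannot exceed 450 ms unless QT does. This needs no reference range. Under the assumed range, QRS would have to rise by more than 450 − 120 = 330 to 450 − 80 = 370 ms to leave the lowest class.

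**PR values.** Under the assumed range, PR would have to rise by more than 450 − 200 = 250 to 450 − 120 = 330 ms.

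**PR and QRS changes.** Increases above 30 ms are registered. An increase of exactly 30 ms stays in the lowest class. Under the same assumption it is 30/200 = 15% to 30/120 = 25% of PR, and 30/120 = 25% to 30/80 = 37.5% of QRS.

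**The case against.** The strongest reply is that the printed limits were meant for QT and QTcF only, with parameter-specific limits intended for 7.5. The dead pointer makes that plausible, and the table templates, which are a separate document, might settle it. But 7.5 is empty, so on that reading RR, PR and QRS are to be described in classes that are defined nowhere. The section needs correcting either way.

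A second reply is that SAP 3.1 already secures numeric summaries: "Quantitative data: number of observed values, mean and standard deviation, median, first and third quartiles, minimum and maximum", followed by a further general rule for continuous variables. Section 3.5.4 also describes changes from baseline for classed vital signs without giving change classes, so there the word classes need not exclude numbers. This has weight, and numeric output may well be produced. The conflict with the wording of 3.5.5 remains, and numeric output would not make the class tables informative.

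Third, a one-sided lowest change class is the protocol's own choice for QTc. That is fair as regards QTc. For PR and QRS the loss is partial, since larger increases are shown. For RR it misleads, although the separate heart-rate classes carry much of the same information.

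Finally, the consequence is small. The SAP covers a single-arm lead-in of about 25 planned participants, with few scheduled ECGs (inclusion, C1D1 if baseline is more than 7 days old, and C2D1). ECG intervals are not among the endpoints listed for that part, and ECG findings the investigator considers clinically relevant are reported as adverse events. All of this stands and sets the severity.

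**Conclusion.** The concern holds and is minor. As written, SAP 3.5.5 applies one set of QTc limits to five intervals, departs from protocol 10.1.2.6.3.2, and cites a section that contains no thresholds. The RR result is arithmetic and the QRS result follows from the protocol's definition of QT. The PR result, and the sizes quoted for PR and QRS, rest on the assumed baseline ranges, though any PR below 450 ms falls in the same class. Whether numeric summaries will also appear cannot be settled from the text.

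The effect is limited to descriptive safety tables. The DLT rule does not use them, QTcF keeps the protocol's classes and heart rate has its own. Still, safety is the primary objective of the part being reported, and these tables would be uninformative for PR and QRS values and misleading for RR.

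**What to change.** In SAP 3.5.5:
- Restrict the 450/480/500 ms and 30/60 ms classes to QTcF, in line with protocol 10.1.2.6.3.2. Uncorrected QT may stay if labelled as an addition to the protocol.
- State that RR, PR and QRS are described as quantitative values at baseline and last value, and as change from baseline, with the SAP 3.1 statistics.
- Remove the pointer to 7.5, or place the thresholds there.

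The cost is one SAP sentence and a table shell. The intervals are already collected as numbers, so no new data are needed.

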3.6. QoL

Not applicable

4. INTERIM ANALYSIS

Not applicable.

5. APPENDIX A: DATA HANDLING AND PROGRAMMING SPECIFICATIONS

5.1. General analytic definitions

5.1.1. Expressions

Reliable value for biological and coagulation samplings is identified in datasets with flag *BIOFG_parameter name* (“Non analysable value”) different from 1 and non-missing result. For other panels, **reliable value** is a non-missing result.

Value at baseline is defined as the last reliable value prior to treatment intake.

Note: In case of patient included and/or randomised but not treated (*i.e.* patients with treatment duration equal to 0): value at baseline is defined as the last reliable value.

Post-baseline value is defined as a reliable value after the first study treatment intake.

Last value is defined as the last reliable post-baseline value of the criteria of interest during treatment period.

Withdrawal value is defined as the reliable value of the criteria of interest during the withdrawal visit.

Lowest value is defined as the lowest value during the treatment period.

Highest value is defined as the highest value during the treatment period.

Worst (lowest/highest) value at cycle *i* is defined as the worst (lowest/highest) value at cycle.

5.1.2. Value prior to treatment / under treatment

Table (5.1.2) 1 - Time frame

Criteria	Value prior to treatment if measured between (D1 =) days before and (D2 =) days after the first treatment intake (D1 and D2 included)		Post-baseline value on studied/interest period if measured between (D1 =) days after the first treatment intake and until (D2 =) days after the last treatment intake as defined in Section 5.1.5 (D1 and D2 included)	
Tumour assessment (all lesions)	D1 = 28	D2 = Xsup	D1 = Xinf	D2 = 30
Biochemistry/haematology/ coagulation/urinanalysis	D1 = 7	D2 = Xsup*	D1 = Xinf*	D2 = 30
Vital signs and physical examinations	D1 = 7	D2 = Xsup*	D1 = Xinf*	D2 = 30
Pregnancy test	D1 = 7	D2 = Xsup	D1 = NA	D2 = NA
ECG	D1 = 28	D2 = Xsup	D1 = Xinf	D2 = 30
Concomitant treatment	D1 = -∞	D2 = Xsup	D1 = Xinf	D2 = 0
AE expected	D1 = -∞	D2 = Xsup	D1 = Xinf	D2 = 30

Xsup: 0 and "Visit< "C001"

Xsup*: 0 and "Visit≤ "C001" where DAY≠ unscheduled

Xinf: 0 and "Visit ≥ "C001"

Xinf*: 1 and "Visit ≥ "C001", (Note: C001 DAY = unscheduled is considered as a post-dose assessment when reported the same date as the first treatment intake)

Table (5.1.2) 2 - Time frame of cycle n

Notations	Definitions
	Start date: First IMP intake date of cycle n
	End date: The day before the 1 st IMP intake of cycle (n+1) ➢ It means that assessments planned the same day but before the 1 st IMP intake in cycle (n+1) are part of cycle n.
Cycle n	For the last cycle, End date = min (first IMP intake date, date of death).

(*)
max (first intake date of trifluridine/tipiracil of last cycle + 27 days, first intake date of futuximab/modotuximab of last cycle + 27 days) The Data Management variable VISIT in exposure dataset will be used to determine the start date of each cycle.

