4. Tumour measurements: tumour assessments should be performed according to RECIST version 1.1. The same method of assessment and the same technique must be used for all evaluations. To include diagnostic imaging by CT or magnetic resonance imaging (MRI) of the chest, abdomen and pelvis, and other sites as indicated based on tumour location and clinical judgment in order to assess the status of the underlying malignancy. Use of contrast is preferred but is at the discretion of the investigator, as medically indicated. At each time point, obtain imaging-based evaluation of the chest, abdomen, and pelvis at a minimum (other localisations if clinically indicated).
 - a. Baseline: tumour assessment will be done within 28 days prior to the first administration of first IMP. Images obtained prior to participant signed informed consent form (ICF) may be used if the date of the images is within 28 days of randomisation (first administration of first IMP for Safety Lead-In part) and if in line with methods and techniques that will be used during study
 - b. Treatment period: tumour assessments will be done every 8 weeks from C1D1 (\pm 7 calendar days) until radiologic progression is documented
 - c. Withdrawal visit: tumour assessments will be performed only if not performed within previous 8 weeks. Every effort should be made to perform the WV tumour assessments prior to the start of new anti-cancer therapy
 - d. Follow-up period: unless patient had discontinued study treatments for radiologic disease progression or withdrawal of consent, obtain tumour assessments within 8 weeks after the last previous tumour assessment and then every 8 weeks (\pm 10 calendar days) until documentation of radiologic disease progression, regardless of initiation of a new anticancer therapy
5. Vital signs: Vital signs including body temperature, pulse rate, respiratory rate, blood pressure, oxygen saturation by pulse oximetry
6. Study procedures prior to the first IMP administration: to be done at C1D1 prior to the first IMP administration only if baseline procedures have been done more than 7 days prior to C1D1
7. Study procedures obtained within 48 hours prior to study treatments administration
8. Pregnancy testing
 - a. Pregnancy testing at screening period: with serum β HCG test only (Within 7 days prior to first administration of first IMP)

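### The SAP's ECG window labels a scheduled pre-dose C1D1 ECG as post-baseline, and the ECG tables show only the last value, so a QTc peak that resolved is not tabulated

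*SAP*

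**What the plan says.** SAP 5.1.1 sets the general definitions. A baseline value "is defined as the last reliable value prior to treatment intake"; a post-baseline value "is defined as a reliable value after the first study treatment intake".

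SAP Table (5.1.2) 1 turns these into windows by data type. The ECG row uses the un-starred limits. Its pre-treatment window runs from 28 days before first intake up to "Xsup: 0 and 'Visit< 'C001". Its post-baseline window starts on day 0 for any visit from C001 onward. The laboratory and vital-sign rows use the starred limits: the pre-treatment window admits visit C001 if it is scheduled, and the post-baseline window starts on day 1. A note treats an unscheduled C001 record dated on the day of first intake as post-dose.

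The protocol has a pre-dose ECG at C1D1 (Section 8.2.6 and the Lead-In schedule, Table (4.1.2) 1). Footnote 6 of that schedule makes it conditional: "to be done at C1D1 prior to the first IMP administration only if baseline procedures have been done more than 7 days prior to C1D1". Laboratory data and vital signs carry the same condition.

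For reporting, SAP 3.5.5 says ECG parameters "will be described by classes, in terms of value at baseline and last post-baseline value under treatment", and SAP 7.5 derives one change only: "Change from baseline to last visit = Last absolute prolongation - Absolute prolongation at baseline". For vital signs, SAP 3.5.4 also includes "worst value under treatment and last post-baseline value under treatment", and SAP 3.5.3 has shift tables to the worst laboratory value. The protocol's own ECG analysis (10.1.2.6.3.2) planned "value at each post-baseline visit under treatment and last post-baseline value under treatment".

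**The concern.** Two parts of the SAP give opposite labels to the same record. A programmer following Table (5.1.2) 1 will discard the ECG closest to first dose as a baseline and may report it as an on-treatment result. Nothing in the SAP explains why ECG should differ from laboratory and vital-sign data here.

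The last-value rule is a separate matter. The QTc classes go up to values above 500 ms and changes above 60 ms, so they exist to show large prolongations. Protocol 8.2.6 delays dosing when QTc exceeds 480 ms, and Appendix 11 makes restart after a Grade 3 prolongation depend on QTc recovery. The last ECG of a participant who had a prolongation can therefore be a recovered one. With the Randomised part cancelled and only the primary safety analysis and best overall response retained (SAP 1.1), the safety tables are the main output of the study.

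**Working it through.** The plan states no figure on this point, so the check applies the rules as written.

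**1. Window logic.** Day 0 is the date of first intake. Current limits: pre-treatment if day ≤ 0 and visit before C001; post-baseline if day ≥ 0 and visit C001 or later. Starred limits: pre-treatment if day ≤ 0 and visit up to C001, scheduled; post-baseline if day ≥ 1 and visit C001 or later, plus the note on unscheduled C001 records. The look-back is 28 days in both columns.

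| ECG record | Current ECG limits | Starred limits | SAP 5.1.1 |
|---|---|---|---|
| Inclusion, day -20 or -8 | pre-treatment | pre-treatment | pre-treatment |
| C001 scheduled pre-dose, day 0 | **post-baseline** | pre-treatment | pre-treatment |
| C001 scheduled, day -1 | **neither** | pre-treatment | pre-treatment |
| C001 unscheduled, day 0 | post-baseline | post-baseline | depends on time of recording |
| C002, day 28 | post-baseline | post-baseline | post-baseline |

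Only the scheduled C001 ECG changes class, and the starred limits agree with 5.1.1 for it. Protocol 8.2.6 schedules no post-dose ECG at C1D1, so the starred limits would not pull a scheduled treated ECG into baseline.

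**2. Effect on one participant (assumed QTcF values).** Inclusion, day -10: 430 ms. C1D1 pre-dose: 455 ms. C2D1: 495 ms. Later unscheduled ECG: 440 ms.

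- Baseline is 455 under 5.1.1 and 430 under the table.
- Change to last value is 440 - 455 = -15 ms, or 440 - 430 = +10 ms. Both fall in the ≤ 30 class, and the last value falls in the ≤ 450 class.
- The 495 ms peak belongs in the 480 to 500 class. Its change is 495 - 455 = +40 ms (30 to 60 class) or 495 - 430 = +65 ms (> 60 class). Under SAP 3.5.5 and 7.5 it enters neither the last-value table nor the change to last value.
- If no ECG followed C1D1, the tabulated last value under treatment would be 455 ms with a change of 455 - 430 = +25 ms, although both ECGs were untreated.

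**3. Effect on class percentages.** Suppose k of the planned 25 participants have a C1D1 ECG and none later (assumed range 0 to 5). They wrongly sit in the post-baseline denominator. One participant in a class is 1/25 = 4.0% with them included. With them removed it is 1/24 = 4.2% for k = 1, rising to 1/20 = 5.0% for k = 5.

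**4. How often the last ECG is not the highest.** If a participant's m on-treatment ECGs are exchangeable (an assumption), the probability is 1 - 1/m: 0% for m = 1, 50% for m = 2, 66.7% for m = 3, 75% for m = 4. Not every such case changes a class.

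**The case against.** On the window, the case against is about reach. First dose should follow inclusion within 3 days, and an ECG is planned at inclusion. An ECG done at that visit is under 8 days old and needs no repeat at C1D1. Only participants with an older screening-period ECG are affected, plus any for whom a site repeated the ECG without needing to; for the latter the earlier ECG may be fresher than 8 days. The day -1 record is an edge case, since footnote 6 places the repeat at C1D1. The untreated value becomes the last value only if no later ECG exists, and C2D1 is scheduled. All of this stands and limits the size; none of it removes the conflict between 5.1.1 and the table.

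On the last-value rule, the restriction was deliberate: the SAP's version 2.0 log records it, after the Randomised part had been cancelled. The second sentence of 3.5.5 gives QT classes without naming a time point, 5.1.4 mentions QT per measurement time, and the output templates are in a separate document. A clinically relevant QTc prolongation should be reported as an adverse event, and SAP 3.5.1 tabulates those by worst grade and action taken. If C2D1 is the only on-treatment ECG, then m = 1 and nothing is missed. These points are fair. However, the untimed sentence and the 5.1.4 remark do not create a peak-value or by-visit table. The adverse-event route depends on reporting and does not show the QTc classes. A deliberate restriction that drops the by-visit tables without adding a worst value still leaves ECG with less than laboratory and vital-sign data receive.

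**Conclusion.** Both parts hold. The ECG row of Table (5.1.2) 1 is wrong as written: it contradicts SAP 5.1.1 and the treatment of other data collected under the same repeat rule. The main consequence is for individual change from baseline. Where the C1D1 repeat was required, the reference is an ECG 8 to 28 days old instead of the pre-dose value. The effect on class percentages is small, 4.0% against 4.2% to 5.0% per participant, under an assumed k of 1 to 5 and the planned 25. The study stopped during the Lead-In, so the true denominator may be smaller. The number of participants with a C1D1 ECG is not in the documents.

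The last-value rule leaves the ECG tables unable to show a resolved peak in anyone with two or more on-treatment ECGs. The 50% to 75% figures for m = 2 to 4 rest on exchangeability and count misses of the maximum, not changes of class. This should be corrected. It affects no hypothesis test, and the Lead-In decision uses DLT counts and the monitoring committee's review of all safety data.

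**What to change.** 1. In the ECG row of SAP Table (5.1.2) 1, replace Xsup and Xinf with Xsup* and Xinf*, keeping the 28-day look-back.
2. In SAP 3.5.5 (and the derivation in 7.5), add the highest post-baseline QTcF under treatment and its change from baseline to the class tables, beside the last value. State that this maximum uses scheduled and unscheduled ECGs, so that the scheduled-only rule in 5.1.4 is not read as applying to it.
3. Report the number of on-treatment ECGs per participant, because a maximum rises with the number of recordings.
4. Reconcile the ECG time points. The ECG row of the Lead-In schedule, Table (4.1.2) 1, appears to carry a further pre-dose mark from Cycle 3 onward, although the table is broken in the text available. Protocol 8.2.6 lists only inclusion, C1D1, C2D1 and clinical indication.

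The cost of the SAP changes is two table cells and one added block of ECG output, with the count of ECGs beside it. All the data are already collected.

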3.4. Endpoints

The study endpoints for the Safety Lead-In and Randomised parts are listed in [Table \(3.4\) 1](#) and [Table \(3.4\) 2](#) respectively.

Table (3.4) 1 - Endpoints for the Safety Lead-In Part

	Objectives	Endpoints
Primary	To assess safety and tolerability of futuximab/modotuximab in combination with trifluridine/tipiracil according to National Cancer Institute Common Terminology Criteria for Adverse Events (NCI-CTCAE) v5.0	
 - Incidence of dose-limiting toxicities (DLTs) - Incidence, severity and relationship of Treatment Emergent Adverse Events (TEAEs) and Serious Treatment Emergent Adverse Events (STAEs) - AEs leading to dose interruption, modification, delays and permanent treatment stop - Changes from baseline in key laboratory safety assessments, and vital signs

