6.1.2. Premedication before futuximab/modotuximab administration

6.1.2.1. Premedication for Infusion-Related Reactions

6.1.2.1.1. Infusion-Related Reactions

There is an inherent risk for infusion-related reactions (IRRs) with the administration of mAbs. An IRR is defined as an AE occurring during the futuximab/modotuximab infusion and up to 24 hours after the end of infusion (EoI), which is assessed by the investigator to be related to the infusion. Signs and symptoms of IRRs may include but are not limited to:

- Facial flushing and swelling.
- Rash including urticaria.
- Headache.
- Fever.
- Chills, rigors.
- Diaphoresis.
- Tachycardia.
- Hypotension.
- Nausea.
- Dry mouth.
- Chest/back/abdominal pain/discomfort.
- Chest and throat tightness.
- Shortness of breath.
- Cough, wheeze, stridor.
- Hypoxia.
- Bronchospasm.
- Laryngeal edema.
- Angioedema.
- Shock.

The risk of an IRR is highest for the first administration of a mAb and diminishes with subsequent infusions. If an IRR occurs, it should be classified according to the NCI-CTCAE v5.0.

Guidelines for grading and management of IRRs of all severities are provided ([Appendix 9](#)).

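### The SAP's time-frame table turns the scheduled Cycle 1 Day 1 end-of-infusion vital signs into the baseline value

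*SAP*

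**What the plan says.** SAP 5.1.1 defines the value at baseline in words: it "is defined as the last reliable value prior to treatment intake". The same section makes any reliable value after first intake post-baseline.

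SAP 5.1.2 then sets the operational windows. The row "Vital signs and physical examinations" opens the prior-to-treatment window 7 days before first intake and closes it at a limit called Xsup*. That limit admits day 0 and any visit up to and including C001, "where DAY≠ unscheduled". The post-baseline window for the same row opens at Xinf*, one day after first intake. A note gives the single same-day exception: "C001 DAY = unscheduled is considered as a post-dose assessment when reported the same date as the first treatment intake". SAP 5.1.5 defines first intake as a date, not a time.

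Protocol 8.2.1 and Table (4.1.2) 1 place two vital-sign readings on Cycle 1 Day 1. One is pre-dose, taken only if the baseline set is more than 7 days old. The other is at the end of the infusion, within 5 minutes either way. Protocol 6.1.1.3 puts the infusion after the trifluridine/tipiracil intake.

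The primary endpoints of the Safety Lead-In (Protocol Table (3.4) 1) include "Changes from baseline in key laboratory safety assessments, and vital signs". SAP 3.5.4 summarises vital signs at baseline, at the cycle 1 worst value, at the overall worst value and at the last value, the last three all under treatment, with changes from baseline.

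**The concern.** The end-of-infusion reading is taken after the first dose of both drugs, yet it meets every condition of the prior-to-treatment window: day 0, visit C001, not unscheduled. Because baseline is the last value in that window, this reading displaces the inclusion or pre-dose value.

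The note on unscheduled records shows that the authors considered same-day post-dose data but covered only part of it. The date rule is harmless for weight, ECOG status and laboratory tests, whose scheduled Day 1 assessments are all pre-dose. Vital signs are different.

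This reading also carries particular weight. The protocol states: "The risk of an IRR is highest for the first administration of a mAb". It lists fever, tachycardia, hypotension and hypoxia among the signs of a reaction. All later scheduled vital signs at treatment visits are pre-dose, so the Day 1 end-of-infusion reading is the only scheduled one that can show an acute infusion effect. Under the table it becomes the reference from which other effects are measured.

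**Working it through.** The plan gives no figure to reproduce; this is a classification rule, so the check applies the rule to the protocol's own schedule. It assumes that the end-of-infusion record carries the Cycle 1 visit code and is not flagged unscheduled, as its place in the schedule implies.

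**Step 1: apply both sections to each record.**

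| Record | Day from first intake | Scheduled? | Table (5.1.2) 1 | Wording of 5.1.1 |
|---|---|---|---|---|
| Inclusion, within 7 days | before 0 | yes | prior | prior |
| C1D1 pre-dose, if taken | 0 | yes | prior | prior |
| C1D1 end of infusion | 0 | yes | **prior** | **post-baseline** |
| C1D1 unscheduled | 0 | no | post | depends on clock time |
| C1D8, C1D15, C1D22 pre-dose | 7, 14, 21 | yes | post | post-baseline |

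The third row is where the sections conflict for a scheduled record. The last prior record under the table is the end-of-infusion reading, whether or not a pre-dose reading was taken that day.

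**Step 2: general size of the error.** Let the pre-dose level be b and the end-of-infusion value b + d. For a later value y:

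- change under the table = y − (b + d)
- correct change = y − b
- error = −d, for every later value

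The documents give no size for d. Taking an assumed range of −30 to +30 units, with b = 120 and later readings back at 120:

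| d | Baseline under table | Change at later readings, table | Correct later change | Correct end-of-infusion change (not reported under table) |
|---|---|---|---|---|
| −30 | 90 | +30 | 0 | −30 |
| −20 | 100 | +20 | 0 | −20 |
| −10 | 110 | +10 | 0 | −10 |
| 0 | 120 | 0 | 0 | 0 |
| +10 | 130 | −10 | 0 | +10 |
| +20 | 140 | −20 | 0 | +20 |
| +30 | 150 | −30 | 0 | +30 |

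**Step 3: one participant, assumed values.** Systolic pressure is 130 at inclusion, 88 at end of infusion and 126 at Day 8, with no other cycle 1 reading below 126.

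- Under the table: baseline 88; cycle 1 lowest value 126; change 126 − 88 = +38; no on-treatment value in the class below 90 mmHg.
- Correctly classed: baseline 130; cycle 1 lowest value 88; change 88 − 130 = −42; one on-treatment value in the class below 90 mmHg.

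The drop is reported as a rise, and the class count of SAP 3.5.4 moves from on treatment to baseline.

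**The case against.** The strongest reply is that this is a conflict between two sections, not a settled error: a programmer who followed 5.1.1 and used clock times would class the reading correctly. That is true, but the SAP does not say that 5.1.1 overrides the table, and the table is the section that gives the programmable limits. No time-point or clock-time rule elsewhere resolves it.

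A second reply is that Table (5.1.2) 2 starts cycle 1 on the first-intake date, so the reading is in cycle 1 by date. But SAP 3.5.4 asks for the cycle 1 worst value under treatment, and Table (5.1.2) 1 excludes the reading from that period.

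Third, infusion reactions are still collected as adverse events, and a Grade 3 or higher reaction counts as a dose-limiting toxicity. Unscheduled readings taken that day count as post-dose. The scheduled value would still be visible, as a baseline value. All of this stands: the reading is mislabelled in the vital-sign tables, but the safety signal is not lost from the study.

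Fourth, the tables are descriptive, the lead-in has one arm, the enrolment thresholds use dose-limiting toxicity counts, and SAP section 1 records that the randomised part was cancelled. This also stands. It limits the consequence but does not make a post-infusion reading a valid baseline.

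Finally, the number actually treated is not given, and the numerical examples are assumptions. If the end-of-infusion value equals the pre-dose value, both rules agree.

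**Conclusion.** The concern holds. As written, Table (5.1.2) 1 makes the scheduled Day 1 end-of-infusion vital signs the baseline and removes them from the on-treatment summaries, against the wording of SAP 5.1.1. The error in each later change is −d, where d is the shift at end of infusion. It is systematic across all participants with that reading, up to everyone treated (about 25 planned). Its actual size cannot be found from the documents.

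The affected output is the vital-sign part of the Safety Lead-In's primary safety endpoint. SAP 1.1 retains only the primary analysis and best overall response, so this is part of what the trial will report. The conclusion rests on reading the table literally and on the visit coding assumed above. Adverse-event and dose-limiting-toxicity reporting is not affected.

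**What to change.** In Table (5.1.2) 1, give vital signs their own row keyed to planned time point:

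- The C1D1 pre-dose reading is prior to treatment.
- The C1D1 end-of-infusion reading is post-baseline and enters the cycle 1 worst value and the overall worst value.
- The existing date rule stays for weight, ECOG status and laboratory tests.

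Add a sentence that the definitions in 5.1.1 govern wherever a date window would place a post-intake value before treatment. Keying on planned time point avoids any need for vital-sign clock times, which the protocol does not clearly require. It does need the dataset to distinguish the two Day 1 readings, as the protocol schedule already does; the sponsor should confirm this.

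The cost is one table row, one sentence and a change to the baseline flag. The SAP's page on documentation of statistical methods describes the analyses as already performed. The sponsor should therefore check which Day 1 record was flagged as baseline, and rerun the vital-sign tables if it was the end-of-infusion reading.
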